
Follow up Objectives
	
Follow up Endpoints - Data from month 36 (if available) or final follow-up. This will only be applicable for patients past month 24

 To assess long term safety follow-up with otelexizumab treatment. 	
 Significant adverse events. Severe (as per ADA classification, Appendix 7) hypoglycemic events which occurred following Month 24 visit (if available) until final follow-up. Severe hyperglycemic events which occurred following Month 24 visit (if available) until final follow up. Mean daily insulin use over 7 consecutive days preceding the call. HbA1c results around time of the phone call.

*Samples will be collected and only analysed after review of safety endpoints
	

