3.3.1.2. Study Duration

Data from the literature at the origin of the study design identified a causal relationship between the degree of immunosuppression and an increased incidence of EBV related Post Transplant Lymphoproliferative Disorders (PTLD) and for this reason a long-term follow-up (60 months) was implemented at the start of the study. The interim analysis data which emerged from this study showed a prompt regain of immune competence observed in treated subjects and consequent rapid resolution of EBV reactivation, both clinically and virologically. The long term EBV related PTLTD risk, as observed in solid organ transplant on a chronic immune suppression therapy, is negligible. As a result, the overall study duration for each subject will be 24 months, except for those patients who have already passed the 24 month or 36 month follow up, in which case they will have a final follow up communication (telephone call or visit) as soon as possible following approval of this amendment 08 of the protocol. Further details are provided in the Study Reference Manual (SRM). If further follow up is required, the Investigator will request that the patient visits the site. See Section 9.3 for a description of analysis considerations.

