7. SAFETY ANALYSES

The safety analyses will be based on the “Safety” population, unless otherwise specified. Due to the long duration of the study safety summaries will be presented for the following time spans: Overall, Dosing Period (defined as day of first dose up to and including day of last received dose of study drug), Post dose up to Week 6, Post-Week 6. A definition is found in Section [11.3](#).

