11.3. Appendix 3: Study Phases

11.3.1. Study Phases

Assessments and events will be classified according to the time of occurrence relative to dosing.

Study Phase	Definition
Pre-Treatment	Date < Date of First Dose
During Dosing	Date of First Dose <= Date <= Date of Final Dose + 1.
Post-dose to Week 6	Date of Final Dose + 1 < Date <= Date of Week 6 Visit ^[1] or Day 42 whichever is greater
Week 6 to Month 24	Date of Week 6 Visit ^[1] or Day 42 whichever is greater < Date <= Month 24 visit.
Safety Follow-up	Date > Month 24
[1] For participants who were consented Prior to Protocol Amendment 4, Day 42 will be used, as they will not have a Week 6 visit.	

Note: for any rule that is relative to dose, the term date also includes time, if recorded. The end date for a visit as recorded in the SV domain will be used for the determining study phase.

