AE = Drug-related	➤ If relationship is marked 'YES' on eCRF OR value is missing.								
Adverse Events : CRS and Clinical Symptoms of Mononucleosis Definition									

 The current MedDRA version at time of database lock will be used for coding of AE's. AEs considered to be related to CRS during the first 14 days post first dose will be determined by medical expert review conducted by the GSK team. For reporting of clinical symptoms of mononucleosis, the following AE's will be extracted based on Preferred Term. In addition, other terms maybe included at the time of reporting. 									
	
  
 Reporting	Preferred Term	Verbatim Terms	
   
 Clinical	Fatigue	Feeling tired & Low energy	
  
	Reporting	Preferred Term	Verbatim Terms	Clinical	Fatigue	Feeling tired & Low energy		
Reporting	Preferred Term	Verbatim Terms							
Clinical	Fatigue	Feeling tired & Low energy							

Adverse Events		
General		
Symptoms of Mononucleosis	Malaise	Feeling unwell
	Myalgia	Joint and muscle pain & Flu like symptoms
	Oropharyngeal pain	Sore throat, throat pain
	Lymphadenopathy	Swollen glands
	Pyrexia	High temperature, Feeling hot and cold & Shivering

Laboratory Parameters

 • All BLQ values will be imputed with $\frac{1}{2}$ LLOQ. • All ALQ values will be imputed with the ALQ + [smallest positive number with the same number of decimal places as the ALQ is reported with] • Values reported as < x are assumed to have an LLOQ of x. • Values reported as > x are assumed to have an ALQ of x.

EBV				

 EBV Serology: 
 Categories (negative, positive) will be derived from absolute IgG and IgM values according to a worst case approach from absolute virus results 				
	QUEST Classification of INDEX	Quest classification of U/ml	BDR Classification of AE/mL	Unified Classification
IgG	< OR = 0.90 NEGATIVE 0.91 - 1.09 EQUIVOCAL > OR = 1.10 POSITIVE		negative : <20 positive : 20 or more	NEGATIVE POSITIVE POSITIVE
IgM	< OR = 0.90 NEGATIVE 0.91 - 1.09 EQUIVOCAL > OR = 1.10 POSITIVE	negative: <36 positive: 36 or more	negative : <20 weakly positive : 20-40 positive : 40 or more	NEGATIVE POSITIVE POSITIVE POSITIVE

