11.10.5. Safety Tables

Safety: Tables					
No.	Population	IDSL / TST ID / Example Shell	Title	Programming Notes	Deliverable [Priority]
AE					
2.01.	Safety	AE13	Adverse Event Overview	Split as described in Section 11.3	FA (SAC)
2.02.	Safety	AE15	Summary of All Adverse Events by System Organ Class and Preferred Term	Split as described in Section 11.3 Add a "Any Event" category for each SOC even if not in shell	FA (SAC)
2.03.	Safety	AE15	Summary of Drug-Related Adverse Events	Split as described in Section 11.3 Add a "Any Event" category for each SOC even if not in shell	FA (SAC)
2.04.	Safety	AE16	Summary of Serious Adverse Events by System Organ Class and Preferred Term	Split as described in Section 11.3	FA (SAC)
2.05.	Safety	AE1	Summary of AEs Leading to Permanent Discontinuation of Study Drug or Withdrawal from Study	Do not split this output by phase	FA (SAC)
2.06.	Safety	AE5	Summary of All Adverse Events by Maximum Grade by System Organ Class and Preferred Term	Split as described in Section 11.3	FA (SAC)
2.07.	Safety	AE5	Summary of Drug-Related Adverse Events by Maximum Grade by System Organ Class and Preferred Term	Split as described in Section 11.3	FA (SAC)
Cytokine Release Syndrome					

2.08.	Safety	AE15	Summary of Adverse Events - Cytokine Release Syndrome Induced Symptoms	
 • Definition of Cytokine Release Syndrome in Section 11.5.3 • Overall only, not split by study phase. 	FA (SAC)
Epstein-Barr Virus					
2.09.	Safety	AE15	Summary of Adverse Events Considered to be Potentially Associated with EBV Reactivation	
 • Clinical Symptoms of Mononucleosis AE Terms to include are in Section 11.5.3 • Overall only not split by study phase. 	FA (SAC)
2.10.	Safety	Non-Standard SAFE_T3	Summary of categorical values of Epstein-Barr Virus (Serology: IgG & IgM)	
 • Categories (negative, positive) to be derived from absolute values according to a worst case approach as described in Section 11.5.3 	FA (SAC)
2.11.	Safety	Non-Standard SAFE_T2	Summary of Epstein-Barr Viral Load (PCR)	
 • Geometric Means 	FA (SAC)
2.12.	Safety	Non-Standard SAFE_T4	Categorical Summary of Epstein-Barr Viral Load (PCR)		FA (SAC)

Labs

2.13.	Safety	LB1	Summary of Laboratory Values	
 Order parameters alphabetically. BY Labtype (1. Chemistry, 2. Haematology) 	FA (SAC)

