			XXXX			X.XXX	X.XXX

Programming Notes : [1] As required to be modified based on data and any applicable IDSL standard principles for listings

Example : OTHER_L3
Protocol : OTX116505
Population : Safety

Page 1 of X

Listing XX
Listing of Immunogenicity Results

Treatment: Placebo

Inv./ Subj.	Age(yrs)/ Sex/ Race	Visit	Date/Time sample Taken	Screening Result	Confirmation Result	Titer
Xxxx/ xxx	XX/ Male/ White	Day -1	DDMMYYYY/Hh:mm	Positive	Positive	X

Programming Notes : [1] As required to be modified based on data and any applicable IDSL standard principles for listings

Example : OTHER_L4
Protocol : OTX116505
Population : Safety

Page 1 of X

Listing XX
Listing of Auto-Antibody Results

Treatment:Placebo

Inv./ Subj.	Age (yrs) / Sex/ Race	Visit	Date	Study Day	Time	Result	Unified Classifica tion
Xxxx/ xxx	27/ Male/ White	Screening	DDMMYYYY	XX	XX:XX	XXXX	XXXX

Programming Notes : [1] As required to be modified based on data and any applicable IDSL standard principles for listings

Example : OTHER_L5
 Protocol : OTX116505
 Population : Safety

Listing XX
 Listing of Hypoglycemic & Hyperglycemic Event Rates

Treatment: Placebo

Inv. / Subj.	Age (yrs) / Sex/ Race	Event Type	Reporting Period	Number of Events	Start/End Date of Reporting Period	Duration of reporting period (months)	Event Rate (1/month)
Xxxx/ xxx	27/ Male/ White	Hypoglycemic	Overall (up to 24 months visit) Post-dose Dosing Period	XXXX	DDMMYYYY/ DDMMYYYY	XXX	XXXX
			Post Dosing Period up to 6 weeks	XXXX	DDMMYYYY/ DDMMYYYY	XXXX	XXXX
			6 weeks to 3 months	XXXX	DDMMYYYY/ DDMMYYYY	XXXX	XXXX

Footnotes:	For the purpose of this listing one month is assumed to have 30 days. Duration of period and event rate will only be calculated if the visit at the end of the reporting period took place.
Programming Notes :	[1] As required to be modified based on data and any applicable IDSL standard principles for listings

Example : OTHER_L6
 Protocol : OTX116505
 Population : Safety

Listing XX
 Listing of Insulin Use

Treatment: Placebo

Inv./ Subj.	Age (yrs) / Sex/ Race	Study Day	Date/Time	Reported Name/ Standardized Name	Dose	Unit	Last Recorded Weight Prior to Intake (kg)	Standardized Dose (IU/kg)
Xxxx/ xxx	27/ Male/ White	XXXX	DDMMYYYY/Hh:mm	XXXXX/XXXXX				
		XXXX	DDMMYYYY/Hh:mm					
		XXXX	DDMMYYYY/Hh:mm					
		XXXX	DDMMYYYY/Hh:mm					
		Day -1						
		Mean Use						

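### The 'Overall' and 'Post-Week 6' AE spans have no end date, so crude AE percentages, Table 2.09 above all, can compare groups with unequal follow-up

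*SAP*

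**What the plan says.** **Time spans.** SAP section 7 says that "safety summaries will be presented for the following time spans: Overall, Dosing Period", then adds one span from dosing to Week 6 and one after Week 6, and points to section 11.3. Section 11.3.1 lists five phases. The last two are Week 6 to Month 24, and Safety Follow-up, defined as "Date > Month 24". It has no entry for 'Overall' and none for an open-ended 'Post-Week 6'.

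**AE displays (SAP 11.10.5).** Tables 2.01 to 2.04, 2.06 and 2.07 carry the note "Split as described in Section 11.3". Table 2.05 (discontinuation or withdrawal) is not split. Table 2.08 (CRS) is marked "Overall only, not split by study phase", and Table 2.09 (events potentially associated with EBV) carries the same instruction. CRS selection is limited by SAP 11.5.3 to "AEs considered to be related to CRS during the first 14 days post first dose". The symptom list for Table 2.09 in the same section has no time limit.

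**Who is followed after Month 24.** Protocol 3.3.1.2 sets the duration at 24 months, "except for those patients who have already passed the 24 month or 36 month follow up", who get one final contact. Of the follow-up endpoints, Protocol section 2 says "This will only be applicable for patients past month 24". The schedule in Protocol 6.2.2 collects AEs at that contact, and SAP 3.2 holds the final analysis until it has taken place.

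**A cap elsewhere.** In SAP 11.11, the listing shell for hypo- and hyperglycaemic event rates (OTHER_L5) labels its first period "Overall (up to 24 months visit". Shell EFF_T3, for the same events, uses time-normalised counts and a denominator for each period. The AE tables have neither.

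**The concern.** AE incidence is a primary endpoint, read across dose groups and pooled placebo. A crude percentage of subjects with an event can only rise with longer observation. If one group is observed for 24 months and part of another for three years or more, the second can show more events with no difference in risk.

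Here the length of observation probably runs with dose order. Extra events would then fall mainly in the lower-dose groups and in part of the placebo pool, which would weaken or mask a true increase with dose. Table 2.09 is the most sensitive display. Fever, sore throat and fatigue occur in anyone over time, and the table has no phase column against which to check the total.

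Table 2.09 has a second problem. The EBV endpoint covers Day 21 to Month 24 (Protocol 2; SAP 2.2), but the table takes fever and myalgia from the first infusion onward. Both are also CRS terms in Protocol Table 5.

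**Working it through.** The documents give no exposure or event calculation for this point, so there is no figure to reproduce. The check has four parts.

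**1. Does longer follow-up run with dose?** Each cohort is reviewed about six weeks after dosing before the next begins (Protocol 9.3.1.2), so calendar order follows dose order. Escalation stopped in Cohort 3 (SAP 2.3). Placebo is pooled over cohorts (SAP 5.1) and so mixes longer and shorter follow-up. Amendment 8 is dated 26 October 2017, so patients first dosed before about late October 2015 were past Month 24. No dosing dates are given for Cohorts 2 and 3, so the dividing line between dose groups cannot be computed.

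**2. How long is the extra follow-up?** The Amendment 2 summary (2 April 2014) describes an event during the first infusion, so that infusion had already happened. From 2 April 2014 to 26 October 2017 is 1,303 days, and 1,303 / 30.4375 = 42.8 months. The first patient, if still followed, therefore had at least 42.8 − 24 = 18.8 extra months. Appendix 8 states that no enrolled patient had reached Month 48, so the extra time at that date runs from 0 to just under 24 months.

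**3. What would that do to a crude percentage?** Assume a constant hazard, equal in all groups, with incidence P24 at 24 months, and let a fraction f of the event rate be captured after Month 24. At T months:

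P(T) = 1 − (1 − P24)^(1 + f(T − 24)/24)

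P24 and f are assumptions, because the documents give neither.

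| P24 | f = 1, T = 36 | f = 1, T = 42 | f = 0.25, T = 36 | f = 0.25, T = 42 |
|---|---|---|---|---|
| 10% | 14.6% | 16.8% | 11.2% | 11.8% |
| 30% | 41.4% | 46.4% | 33.1% | 34.5% |
| 50% | 64.6% | 70.3% | 54.1% | 56.1% |

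For P24 = 30% and T = 36, in a group of 8 all followed that long, full capture adds 8 × (0.414 − 0.300) = 0.9 of a patient. Quarter capture adds 8 × (0.331 − 0.300) = 0.2.

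**4. Which displays are exposed?**
- Exposed on the literal reading: the 'Overall' columns, Table 2.09, and a 'Post-Week 6' column if section 7 is programmed instead of section 11.3.
- Not exposed: the dosing-period and post-dose-to-Week-6 columns, a Week 6 to Month 24 column, and Table 2.08 (14-day window).
- Hardly exposed: Table 2.05, because dosing lasts six days and a patient who reaches Month 24 counts as completed (Protocol 4.6).
- Table 2.09, early end: a fever or muscle pain on an infusion day can appear in both Table 2.08 and Table 2.09.

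**The case against.** The strongest reply is that the plan already separates late events. Six AE tables are split by phases that stop at Month 24 and put later events in their own phase. The one place where 'Overall' has an end, the hypo- and hyperglycaemia listing, caps it at the 24-month visit. The primary objective includes long-term safety, no formal hypotheses are tested, and escalation rested on roughly six-week data. A cumulative total that keeps late events is therefore defensible.

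Much of this stands. It limits the problem to the displays listed above, but it does not remove it. Table 2.09 has no phase split to fall back on, and a label in a listing for other events does not fix the definition for the AE tables.

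Three further objections also hold:
- **Size.** The 42.8 months bounds the first patient only. Late collection may also be lighter, since the follow-up endpoint names significant AEs, although the schedule row says AEs. Full capture in all 8 patients is an upper illustration.
- **Dose.** A reader might infer that only the low-dose cohorts were followed past Month 24. The documents do not say so. Placebo patients of the early cohorts are included, and 27 mg patients are neither confirmed nor excluded.
- **Day 21.** A reader might infer that Table 2.09 should drop every onset before Day 21. Protocol 3.4 places the EBV peak around Week 3, so a hard cut could lose mononucleosis symptoms that begin earlier and persist.

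**Conclusion.** The point holds in a limited form. The SAP leaves 'Overall' and 'Post-Week 6' without an end, late events come only from the earliest-dosed patients, and Table 2.09 as written mixes unequal follow-up and also takes in infusion-day symptoms.

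That 'Overall' counts events after Month 24 is the literal reading, not an explicit statement. That the extra time lies mainly with the lower doses follows from sequential dosing and is probable, not documented. On a 24-month incidence of 30%, the distortion at 36 months runs from about 3 percentage points (quarter capture) to about 11 (full capture), under a constant hazard and with the whole group followed that long.

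A reader might go further and conclude that the primary safety comparison as a whole is confounded with dose. The documents do not support that: the CRS table and the section 11.3 phase columns up to Month 24 are not affected by the later contact, and EBV serology and viral load are summarised by visit.

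**What to change.** - In SAP section 7, define 'Overall' as first dose to the Month 24 visit for every subject, or to a fixed study day where there is no such visit.
- Replace 'Post-Week 6' with the section 11.3 phase Week 6 to Month 24.
- Report later AEs in a separate Safety Follow-up summary, with the number contacted after Month 24 in each group as the denominator.
- End Table 2.09 at Month 24. In Table 2.09 and Listing 22, flag or show separately the AEs already classified as CRS in Table 2.08 and those resolved before Day 21. Do not exclude every onset before Day 21.
- Rates per patient-month are optional once follow-up is capped.

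The cost is SAP wording and a filter in the AE programs. No data are lost, because late AEs stay in the listings.

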7.1. Adverse Events Analyses

Adverse events analyses including the analysis of adverse events (AEs), Serious (SAEs) and other significant AEs will be based on GSK Core Data Standards. The details of the planned displays are provided in [Appendix 10](#): List of Data Displays.

No separate outputs will generated for Common AEs (more than 5% incidence in any treatment group) as the sample size means all occurrences would be considered common. A footnote will be added to the all AE overview, that all categories count as common.

In case of liver monitoring/stopping events, the outputs required by GSK guidelines will be produced. Those output are not listed in Section [11.10](#).

7.2. Adverse Events Related to CRS and EBV Reactivation

Adverse Events associated with Cytokine Release Syndrome (CRS) induced symptoms and events associated with EBV reactivation will be summarised as per section 7.1 as well as summarised in separate outputs.

See Section 11.5.3 for details on selection of AEs related to CRS and EBV reactivation. The details of the planned displays are provided in Section 11.10: List of Data Displays.

7.3. EBV Serology and Viral Load

EBV Serology will be listed and summarised using frequency of positive/negative values at each visit as described in Section 11.5.3

EBV Viral Load will be listed and summarised using summary statistics using a log-10 transformation. Frequency of number of copies per 10^6 PBM Cells will presented as described in Section 11.5.3.

7.4. Cardiovascular Events

Event Specific data will be listed if there are any occurrences of cardiovascular events. If there are no events these listings will not be produced.

7.5. Clinical Laboratory Analyses

Laboratory evaluations including the analyses of Chemistry laboratory tests, Hematology laboratory tests and liver function tests will be based on GSK Core Data Standards. The details of the planned displays are in Section 11.10.

7.6. Other Safety Analyses

The analyses of non-laboratory safety test results including ECGs and vital signs will be based on GSK Core Data Standards, unless otherwise specified. The details of the planned displays are presented in Section 11.10: List of Data Displays.

8. PHARMACOKINETIC ANALYSES

8.1.1. Drug Concentration Measures

Blood sampling time will be related to the start of dosing. Linear and semi-logarithmic individual serum concentration-time profiles and mean (\pm SD) and median profiles will be plotted by treatment.

Serum concentrations of oteelixizumab will be listed and summarised by treatment group and nominal time.

Refer to Section 11.4 for the reporting process and standards.

8.2. Derived Serum Pharmacokinetic Parameters

- Free serum orelizumab pharmacokinetic parameters will be calculated using SAS. Calculations will be based on the actual sampling times recorded during the study.
- From the serum concentration-time data, the pharmacokinetic parameters in [Table 2](#) will be determined for free serum orelizumab, as data permit, for each treatment and for each participant.
- Table 2 Derived Pharmacokinetic Parameters**

Parameter	Parameter Description
C _{max}	Maximum observed serum concentration
t _{max}	Time to C _{max}
AUC(0-τ)	Area under the serum concentration-time curve from time zero over the dose interval

NOTES: Additional parameters may be included as required.

AUC(0-τ) will be calculated using the trapezoidal rule (see section [11.5.4](#)) and will use all timepoints up to and including Day 6, 1 hour post dose.

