5.2. Treatment Assignment

Patients will be assigned to receive either otelixizumab or matching placebo (4:1 ratio), prior to the start of dosing in each cohort by utilizing RAMOS (GSK's Registration and Ordering System). The randomization schedule utilized by RAMOS will be provided by Clinical Statistics (CS), using internal validated software. Once a randomisation number has been assigned it must not be re-assigned.

A description of each regimen is provided in [Table 4](#):

Table 4 Treatment Assignment

Treatment	Cohort	Treatment Description	Daily Dose of Otelixizumab (mg)
A	1	Otelixizumab 9 mg	1.5
B	2	Otelixizumab 18 mg	3
C	3	Otelixizumab 27 mg	4.5
D	4	Otelixizumab 36 mg	6
P	1-4	Placebo	N/A

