9.3.4. Pharmacokinetic Analyses

All free serum orelizumab concentration data will be graphically represented, descriptively summarised and listed appropriately.

Free serum orelizumab concentration time data will be analyzed by non-compartmental methods with WinNonlin Version 6.1 or higher. Calculations will be based on the nominal sampling times recorded during the study. From the serum concentration-time data, the following pharmacokinetic parameters may be determined, as data permit: maximum observed plasma concentration (C_{max}), time to C_{max} (t_{max}), area under the plasma concentration-time curve [$AUC(0-t)$ and $AUC(0-\tau)$], and apparent terminal phase half-life ($t_{1/2}$). Additional parameters may be included as required.

Pharmacokinetic data will be presented in graphical and/or tabular form and will be summarized descriptively. All pharmacokinetic data will be stored in the Archives, GlaxoSmithKline Pharmaceuticals, R&D.

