2.2. Study Objective(s) and Endpoint(s)

Primary	
Primary Objectives (Safety)	Primary Endpoints (Safety)

 To assess the effect of a single course of otelixizumab treatment on the acute and long term safety and tolerability of otelixizumab in NOT1DM patients. 	
 Incidence of adverse events (AEs) particularly those related to Cytokine release syndrome (CRS). Epstein-Barr virus (EBV) reactivation over Day 21 to Month 24. Changes in laboratory values, electrocardiograms (ECGs) and vital signs over Day 14 to Month 24.
Secondary	
Secondary Objectives (Pharmacokinetic)	Secondary Endpoints (Pharmacokinetic)

 To assess the pharmacokinetics of repeat dose administration of otelixizumab over 14 days in NOT1DM patients. 	
 Free serum otelixizumab concentrations over Days 1-14 and summary PK parameters.
Secondary Objectives (Efficacy)	Secondary Endpoints (Efficacy)

 To assess the effect of a single course of otelixizumab treatment on the rate of decline of pancreatic β-cell function over 24 months in NOT1DM patients. 	
 Change from baseline in C-peptide and glucose AUC (0-120) after a Mixed Meal Tolerance Test at Month 3, 6, 12, 18 and 24.

 To assess the effect of a single course of otelixizumab treatment on the rate of decline of C-peptide response and insulin sensitivity of β-cell function determined after a hyperglycemic clamp over 24 months in NOT1DM patients. 	
 Change from baseline in C-Peptide and glucose AUC hyperglycemic phase [H60 to H140 minutes] and insulin sensitivity (IS) index after a hyperglycemic clamp at Months 6 and 24.

 To assess the effect of a single course of otelixizumab treatment on exogenous insulin use for otelixizumab over 24 months in NOT1DM patients. 	
 Change from baseline in mean daily insulin use over 7 consecutive days during the week preceding all visits and phone calls.

 To assess the effect of a single course of otelixizumab treatment on glycaemic control over 24 months in NOT1DM patients. 	
 Change from baseline in HbA1c level. Body weight Day -1, Months 12-24. Hypoglycemic & hyperglycemic events over Months 1-24.

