Multimer Analyses Population	
 Comprises of all Intent-to-treat (Treated) who have available multimer data 	
 Biomarker (Multimer Analysis)
NOTES :		

Population	Definition / Criteria	Endpoint(s) Evaluated

 • Please refer to Appendix 10: List of Data Displays, which details the population for each display generated. • As there are no planned pharmacokinetic analyses, this population will be defined for the next reporting effort. 		

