		Vitals ^{1,2}	X	X		X	X	X	X	X	X	X	X	X	X	X		X					X	
		ECG	X									X												
		PK/CD3 Saturation	X																					
3	C1-C4	Dosing																						
		Vitals ^{1,2}	X	X		X	X	X	X	X	X	X	X	X				X					X	
		ECG	X					X				X												
		PK/CD3 Saturation	X																					

Day	Cohort	Assessment	Pre Dose	0 H	30 M	1 H	2 H	3 H	4 H	5 H	6 H	7 H	8 H	9 H	10 H	11 H	12 H	13 H	14 H	15 H	16 H	
4	C1-C4	Dosing																				
		Vitals ^{1,2}	X	X		X	X	X ³														
		ECG	X			X		X ³														
		PK/CD3 Saturation	X																			
5	C1-C4	Dosing																				
		Vitals ^{1,2}	X	X		X	X	X ³														
		ECG	X			X		X ³														
		PK/CD3 Saturation	X																			
6	C1-C4	Dosing																				
		Vitals ^{1,2}	X	X		X	X	X ³														
		ECG	X			X		X ³														
		PK/CD3 Saturation	X			X																

1. Blood pressure to be taken in triplicate at Pre-dose
2. Vitals to be repeated at 30 min intervals should there be any safety concern
3. If patients are dosed on an out-patient basis on Day 4, 5 and 6, vital signs and ECGs will stop after the 3 hour post dose time point (if the Investigator is satisfied with the clinical status of the patient), if there are any concerns then vital signs and ECGs may be continued as judged necessary by the investigator until the investigator is satisfied

Day	Cohort	Assessment	Preferably within first hour of visit, time to be recorded in eCRF
14	C1-C4	PK/CD3 Saturation	X

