11.10.13. Pharmacokinetic Tables

Pharmacokinetic : Tables					
No.	Population	IDSL / TST ID / Example Shell	Title	Programming Notes	Deliverable [Priority]
PK Concentration					
6.01	Fully Treated	PK01	Summary of Free Serum Otelixizumab Concentration-Time Data by Treatment		FA (SAC)

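### SAP 8.2 labels AUC(0-τ) as a one-interval area but computes it over a nominal 121 h with sparse sampling after Day 1, so the value fits neither its label nor a course-long AUC

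*SAP*

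**What the plan says.** SAP 8.2, Table 2 describes AUC(0-τ) as "Area under the serum concentration-time curve from time zero over the dose interval". The note below the table says it is obtained by the trapezoidal rule, with a pointer to section 11.5.4, "and will use all timepoints up to and including Day 6, 1 hour post dose". Neither place gives τ a number.

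Protocol 9.3.4 lists AUC(0-t) and AUC(0-τ) as two separate parameters, both optional: "the following pharmacokinetic parameters may be determined, as data permit". The SAP keeps only the second name.

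The secondary PK endpoint in SAP 2.2 covers free serum "concentrations over Days 1-14 and summary PK parameters". The notes to SAP Section 4, however, state: "As there are no planned pharmacokinetic analyses, this population will be defined for the next reporting effort". The only PK table in SAP 11.10.13 is the "Summary of Free Serum Otelixizumab Concentration-Time Data by Treatment". The PK figures and the PK listing also show concentrations only.

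**The concern.** The label and the calculation describe different quantities. A reader who trusts the label takes the figure as exposure in one dosing interval, when it contains five intervals and the first hour of the sixth. A reader who goes by the note takes it as exposure over the course. That reading also fails, because from Day 2 to Day 5 there is one sample a day, taken just before the infusion starts. Straight lines between those samples miss each rise and fall.

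The pointer to section 11.5.4 adds a second ambiguity. The trapezoid formula there was written for the mixed-meal and clamp tests and divides the area by the time interval. Followed literally, it does not produce an AUC at all.

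At stake is a derived parameter belonging to a stated secondary endpoint, which could be reported under a name that does not match its content.

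**Working it through.** The documents give no AUC value to reproduce. The window and the sampling pattern come from the documents; the half-lives are assumptions.

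**Inputs**
- Dosing is daily for 6 days (Protocol 3.1; 5.2, Table 4), so τ = 24 h by inference.
- Infusion times (Protocol 3.3.2, Table 1) are 9 h on Day 1 in Cohort 1 and 12 h in the higher cohorts, then 6 h on Day 2, 3 h on Day 3 and 1 h on Days 4-6.
- PK samples (Protocol 6.2.3; SAP 11.1.4) are serial on Day 1, pre-dose only on Days 2-5, and pre-dose plus 1 h on Day 6. The single Day 14 sample lies outside the window.
- Half-life is not given. I assumed 6, 12, 24, 36, 48 and 72 h, with 3 h as an extreme.

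**Window.** From the start of dosing on Day 1 to Day 6 + 1 h is 5 × 24 + 1 = 121 h, and 121 / 24 = 5.04 intervals.

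**Model.** One compartment, linear, unit volume, equal daily doses D. With k = ln 2 / half-life and rate R = D/T, the concentration at time x after the start of an infusion of length T is (R/k)(1 − e^(−kx)) while it runs and (R/k)(1 − e^(−kT)) e^(−k(x−T)) afterwards, summed over doses. The SAP figure is Σ (t[i+1] − t[i])(C[i] + C[i+1])/2 at 0, 0.5, 1, 2, 4, 6, 8, then 9 (9 h infusion) or 12 (12 h infusion), 16, 24, 48, 72, 96, 120 and 121 h. The true areas use a fine grid. Because the Day 1 sampling rows are hard to read in the available text, I also tried other Day 1 times for the 12 h infusion; the 0-121 h ratios moved by no more than 0.001.

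| Half-life (h) | SAP / Day 1 AUC(0-24 h), 9 h infusion | Same, 12 h infusion | SAP / Day 6 interval AUC (120-144 h) | SAP / AUC(0-121 h) |
|---|---|---|---|---|
| 6 | 2.16 | 2.22 | 1.9 | 0.39 |
| 12 | 4.04 | 4.25 | 2.7 | 0.58 |
| 24 | 6.80 | 7.25 | 2.9 | 0.72 |
| 36 | 8.61 | 9.21 | 2.8 | 0.77 |
| 48 | 9.85 | 10.56 | 2.7 | 0.80 |
| 72 | 11.41 | 12.26 | 2.6 | 0.83 |

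At 3 h the ratios are 1.3 (Day 1), 1.3 (Day 6) and 0.25-0.26 (0-121 h).

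**Hand check of the shortfall.** Take a half-life of 24 h, unit dose, a 1 h infusion and steady state. Then k = 0.02888. The concentration added by the end of the infusion is (1 − e^(−0.02888))/0.02888 = 0.986, which decays over 23 h to 0.986 × 0.515 = 0.507. The pre-dose level P satisfies P = P/2 + 0.507, so P = 1.015. The straight-line area between two pre-dose samples is 24 × 1.015 = 24.4. The true interval area is 1/k = 34.6. The ratio is 0.70, in line with 0.72 in the table.

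**Division by time.** If section 11.5.4 is applied in full, the figure is divided by 121. At 36 h with a 12 h first infusion, 9.21 / 121 = 0.076 of the Day 1 AUC numerically, in concentration units.

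**Trapezoid restricted to Day 1.** The estimate divided by the true AUC(0-24 h) is 1.00-1.03 for half-lives of 6-72 h. At 3 h it is 1.09 (9 h infusion) or 1.04 (12 h infusion).

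**The case against.** The note states its window openly, the SAP never says that τ is 24 h, and a reader could take the dose interval to mean the whole dosing period. The label conflict would then shrink. This is possible but weak. Protocol 9.3.4 lists AUC(0-t) beside AUC(0-τ), which points to the usual meaning of τ, and SAP 2.1 reports no change from the protocol's planned analysis. The shortfall against AUC(0-121 h) also remains under that reading.

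Three further objections stand:
- A reader might infer that the value is simply too high, by up to twelvefold. The documents do not support that as an unconditional statement. It requires the undivided area, which the pointer to section 11.5.4 leaves open, and it uses Day 1, the comparator with the largest ratios. Against the Day 6 interval the excess is 1.9-2.9 times.
- The sizes come from assumed half-lives in a linear model. Saturable elimination is not covered.
- The consequence is small. Parameters are derived only as data allow, none has a planned display, and SAP 9.3 places PK/PD analysis outside the plan.

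A reader might also treat the missing PK-parameter display as making the AUC fault more serious. It is a separate reporting gap and says nothing about whether the AUC is correctly defined.

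**Conclusion.** The point holds as a minor one. As written, SAP 8.2 gives a value that does not match its label and does not measure course-long exposure. No other passage reconciles the two statements.

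As an undivided area it exceeds a single-interval AUC and falls short of AUC(0-121 h) at every half-life tried. The size cannot be fixed from the documents: for assumed linear half-lives of 6-72 h it is 2.2-12.3 times the Day 1 AUC and 0.39-0.83 times AUC(0-121 h). The conclusion rests on τ = 24 h, inferred from daily dosing. The shortfall also assumes that pre-dose levels do not fall steeply from day to day, as expected under repeat dosing.

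Nothing here supports the wider inference that safety, dose escalation, efficacy or the planned concentration displays are affected. The effect is confined to one derived secondary PK parameter.

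**What to change.** In SAP 8.2:
- State that AUC(0-τ) is the undivided trapezoid area from Day 1 pre-dose to Day 2 pre-dose (0-24 h), the only interval with serial samples.
- State that the division by time in section 11.5.4 does not apply.
- If the 0-121 h area is kept, call it AUC(0-t), the name already in Protocol 9.3.4, and footnote that Days 2-5 rest on pre-dose samples only.

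Separately, reconcile the Section 4 note that no PK analyses are planned with Section 8.2.

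The cost is SAP wording and one footnote, with no new samples. The drawback is that a Day 1 AUC describes only the first and slowest infusion. Its trapezoid is also slightly high: 0-3% for assumed linear half-lives of 6-72 h, and up to 9% at 3 h.
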